8.2 Patient documentation

The following data will be collected from patients using patient questionnaires. Patient questionnaires will be provided on paper and will be sent to the patient by

8.2.1 Documentation at start

The following data will be filled in by _____ before shipment to the patient:

Centre number	
Patient number	
Demographics	Year of birth

The patient will be asked to complete the following questions:

Observation interval	Date of assessment
Personal data	Marital status? (married / living with partner; married / living apart; single; divorced; widowed)

	
Living in a relationship? (no; yes => for how many years?) Do you have any children? (no, yes => how many?)
 
How many persons are currently living in your household?
 
Do you need regular help to do your housekeeping and for your daily routine? (no, yes)

Education and profession
	
Graduation from school? (none; "Hauptschulabschluss"; "Realschulabschluss"; „Fachhochschulreife oder Abitur“; others)
 
Job training? (none; apprenticeship; full-time vocational school; technical / professional school; advanced technical college; university; others)
 
Employment? (full-time; part-time; unemployed; retired; housewife; on sick leave; others)

Medication intake
	
Daily intake of drugs/tablets apart from the prescribed anti-cancer agent? Number of drugs and tablets per day? (none, unknown)
 
Self reported medication intake (questions from reference): Do you occasionally forget taking of your medicine ? (yes, no)
 
Are you occasionally neglectful concerning your medicine intake? (yes, no)
 
When you feel better, do you occasionally stop taking your medicine? (yes, no) Sometimes when you feel worse, do you stop taking your medicine? (yes, no)
 
Self reported medication intake: There are several types of patients in concern of medication intake. Which of the following describes you best? Intake of medicines takes place... - never, although the doctor prescribed it. - don't like it, only if I remembered it - irregularly, forgotten it over and over - at start regulary, later less - always
 
How do you feel about taking your medication? - never mind

	
- don't like it
 
Why don't you like taking your medication?
 
 - difficulties in swallowing tablets - disturbs my daily routine - reminds me of my disease - other 
Compliance to anastrozole: You were supposed to take one tablet anastrozole per day. However, daily medication intake may be forgotten. How many anastrozole tablets did you actually take from the start of anastrozole therapy until today:
 
 - none - few - less than half - almost the half - more than half - almost all - all

Breast cancer and therapy
	
Do you have the feeling that you have a voice in concern of your breast cancer medication? (no, few, satisfactory, good)
 
Were the effects of the anti-hormone therapy and the scheduled drug explained to you? (no, few, satisfactory, good)
 
Were the side effects of the anti-hormone therapy and the scheduled drug explained to you? (no, few, satisfactory, good)
 
Did you receive any sample of anastrozol? (no, yes, if yes, how many?, I don't know)

Questions on arthralgia occurrence, characteristics and management
	
Did you experience any arthralgias? (yes, no)
 
Did you experience any arthralgias before the start of anastrozole treatment? (no, yes => which medication did you take?)
 
Did you experience any arthralgias since you started anastrozole treatment? (no, yes)
 
Which medication did you take because of arthralgias?
 
Did you consult any doctor because of arthralgias, and in which field did the doctor specify? (general practitioner,

	
number of times; internist, number of times; orthopedist, number of times; rheumatologist, number of times; pain therapist, number of times; gynaecologist, number of times)
 
Which diagnostic measures did you undergo during your doctor`s visit? (X-ray, CT, MRT, Ultrasound)
 
Were you admitted to hospital due to arthralgias?
 
Did you receive any physiotherapy? (yes, no, if yes => therapy method; number of prescribed therapies)
 
Performance of any regular sportive action? If yes, how often?
 
VAS scale: Rheumatoid Arthritis Symptom Questionnaire (see appendix E)

Questions about medication side effects	GASE-P: Generic Assessment of Side Effects (appendix E)
Somatosensory amplification of side-effects	SASS, Somatosensory Amplification Scale (appendix E)
Patient`s belief about medicines	BMQ, Beliefs about medicines questionnaire (appendix E)

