	3 – approximately half	[40% ; 60%]
	4 – more than half	[60% ; 80%]
	5 – almost all	[80% ; 100%]
	6 – all	100%.

3) A patient will only be defined as being ‘compliant’ when the answer of the doctor **and** the patient score ‘5’ or ‘6’ concerning the question regarding the number of tablets actually taken.

Upon receipt of sick fund data, for patients insured in the GWQ and who consented to data exchange, compliance data obtained in this NIS will be compared to the percentage of prescriptions actually received by the pharmacies.

Arthralgias

Arthralgias will be summarized by incidence, localization, onset, duration, intensity, and relationship to study drug, diagnostics and arthralgia management (e.g. medication, physiotherapy, doctor’s visits, change of life style etc.). Arthralgia characteristics will be particularly assessed using VAS scores (Appendices E and F).

Perception of side-effects

Subjective perception of side-effects will be evaluated using the following scores: GASE-P (Generic Assessment of Side Effects, appendices E and F), SASS (Somatosensory

Amplification Scale, appendices E and F), and BMQ (Beliefs about medicines questionnaire, appendices E and F).

Arthralgia therapy and related costs

Arthralgia therapy will be documented in the eCRF and in the patient questionnaire (for further information, see Chapter 8; e.g., newly prescribed medication, doctor's visits, diagnostics, hospital admissions). Diagnostic and therapeutic measures will be recorded as standardised patterns in the eCRF and in the patient questionnaire and will be correlated with itemised costs for evaluation purposes. Cost evaluations will be feasible on patient and global level.

Validation of data (arthralgia therapy and compliance) by sick fund data

For patients who signed an additional informed consent form (Appendix C, see chapter 7.3), arthralgia therapy as documented by the investigators and the patients will be compared to sick fund data on an individual patient level by a third party who will combine the study and the sick fund datasets on an individual patient level. The third party will combine the sick fund dataset and the study dataset using the patient insurance number which will be sent to on the additional informed consent (Appendix C). The patient insurance number will be immediately deleted after data combination. Statistical evaluation will only be based on pseudonymised data.

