5. CENTRE SELECTION AND PLANNED NUMBER OF CENTRES

This NIS study is a non-interventional, multi-centre, observational study with approximately 700 specialised clinics and office based gynaecologists or oncologists. Study Centres will be selected in concern of the criteria of the medical experiences and the knowledge of the disease of study investigators.

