	therapist, number of times; gynaecologist, number of times) Which diagnostic measures did you undergo during your doctor`s visit? (X-ray, CT, MRT, Ultrasound) Were you admitted to hospital due to arthralgias? Did you receive any physiotherapy? (yes, no, if yes => therapy method; number of prescribed therapies) Performance of any regular sportive action? If yes, how often? VAS scale: Rheumatoid Arthritis Symptom Questionnaire (see appendix F)
Questions about medication side effects	GASE-P: Generic Assessment of Side Effects (appendix F)
Somatosensory amplification of side-effects	SASS, Somatosensory Amplification Scale (appendix F)
Patient`s belief about medicines	BMQ, Beliefs about medicines questionnaire (appendix F)

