Subjective perception of side-effects will be evaluated using the following scores: GASE-P (Generic Assessment of Side Effects, appendices E and F), SASS (Somatosensory Amplification Scale, appendices E and F), and BMQ (Beliefs about medicines questionnaire, appendices E and F).

Arthralgia therapy and related costs

Arthralgia therapy will be documented in the eCRF and in the patient questionnaire (for further information, see Chapter 8; e.g., newly prescribed medication, doctor’s visits, diagnostics, hospital admissions). Diagnostic and therapeutic measures will be recorded as standardised patterns in the eCRF and in the patient questionnaire and will be correlated with itemised costs for evaluation purposes. Cost evaluations will be feasible on patient and global level.

Each occurrence of arthralgia will be assigned to the corresponding time interval according to 0-3, 3-6, 6-9, 9-12 and 12+ months after the start of anastrozole treatment (i.e. post treatment start).

Validation of data (arthralgia therapy and compliance) by sick fund data

For patients who signed an additional informed consent form (Appendix C, see chapter 7.3), arthralgia therapy as documented by the investigators and the patients will be compared to sick fund data on an individual patient level by a third party who will combine the study and the sick fund datasets on an individual patient level. The third party will combine the sick fund dataset and the study dataset using the patient insurance number which will be sent to on the additional informed consent (Appendix C). The patient insurance number will be immediately deleted after data combination. Statistical evaluation will only be based on pseudonymised data.

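### The patient questionnaires count arthralgia visits under six specialties without oncologist or 'other', so oncologist visits have no field of their own in the patient source

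*Protocol*

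**What the plan says.** Section 5 describes the centres as "approximately 700 specialised clinics and office based gynaecologists or oncologists". Two office-based specialties therefore act as study physicians.

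The start questionnaire (8.2.1) asks "Did you consult any doctor because of arthralgias, and in which field did the doctor specify". The answer choices, each with a visit count, begin with the general practitioner and continue "internist, number of times; orthopedist, number of times; rheumatologist, number of times; pain therapist, number of times; gynaecologist, number of times". The follow-up questionnaire (8.2.2), due at 3, 6 and 9 months or at treatment discontinuation, uses the same list, ending "therapist, number of times; gynaecologist, number of times".

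The patient questionnaire is a named source for the cost work. Section 3 says that arthralgia therapy is documented in the eCRF and in the patient questionnaire, and gives as examples "newly prescribed medication, doctor's visits, diagnostics, hospital admissions". It continues: "Diagnostic and therapeutic measures will be recorded as standardised patterns in the eCRF and in the patient questionnaire and will be correlated with itemised costs". Section 11.2 adds: "Cost evaluations will be feasible on patient and global level". For women who give the additional consent, the therapy documented by investigators and by patients is to be compared with sick-fund data patient by patient (Sections 3 and 11.2).

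**The concern.** A specialty list in a cost instrument should at least cover the doctors whom the study population is known to see. Every woman in this study is under the care of a study physician, and that physician may be an oncologist. A woman treated by a gynaecologist can report arthralgia visits to her treating doctor under the right heading. A woman treated by an oncologist has no such heading and no open category to use instead.

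Two things can then happen on the form. She may leave the visit out, and the patient-reported count is too low. Or she may enter it elsewhere, for example under internist; the total is then right but the specialty is wrong, and any costing by specialty is wrong with it. Either way, the patient-reported visits would disagree with sick-fund records for a reason built into the form, and the disagreement could be misread as poor patient recall.

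**Working it through.** No arithmetic applies, because the point concerns the answer categories of one item. The check sets the relevant sections side by side.

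1. **Categories offered.** In 8.2.1: general practitioner, internist, orthopedist, rheumatologist, pain therapist, gynaecologist. That is six, with no oncologist and no open category. In 8.2.2: the same six, with the same two gaps.

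2. **Physician types in the study.** Section 5 and the synopsis name two office-based specialties, gynaecology and oncology. One of the two is on the list and the other is not.

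3. **Could the missing open category be an effect of abbreviated writing?** Probably not. The same listing in 8.2.1 prints an open category for schooling, job training and employment; the job-training item ends "advanced technical college; university; others". It also prints one for the reasons for disliking medication, as does 8.2.2. Where an open category was intended elsewhere in this listing, it was written down.

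4. **Is the patient form used for costs?** Yes. Sections 3 and 11.2 name it beside the eCRF, and doctor's visits are among their examples. These sections do not say which source prevails when the two differ.

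5. **Is there a second source for the same visits?** Yes. The investigator's Arthralgia Module at baseline (8.1.2) and at follow-up (8.1.3) asks for doctor's visits together with the doctor's specialty, and no closed list is printed there.

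6. **Does the second source cover women who stop anastrozole?** The treatment discontinuation module in 8.1.3 has its own block on arthralgia and related costs, and that block lists no visit item. However, the Arthralgia Module is separate. It is triggered by arthralgia during anastrozole therapy, and it stands under an introductory line that covers the 3, 6 and 9 month points as well as the time of treatment discontinuation. Nothing in 8.1.3 says that the discontinuation module replaces it.

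Steps 1 to 4 establish the gap in the patient source. Steps 5 and 6 confine it to that source.

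**The case against.** The strongest reply is that the eCRF already captures these visits by specialty. In an oncology practice, the person completing the module is the oncologist visited or a delegate. This stands as far as it goes: the visits are not lost to the study. It does not repair the patient-reported data, which the protocol also uses for costs and for the sick-fund comparison.

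A second reply is that Section 8.2 only summarises a paper form. The form itself is in Appendices E and F, which are not available here, and it may carry an extra line. This also stands as a limit. The point is made on the list as printed in 8.2.1 and 8.2.2, and the appendices should be checked before they are changed.

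A third reply is that the consequence is small. Arthralgia cost is a secondary objective, evaluated descriptively (11.4.1), and the sick-fund comparison covers only consenting women in participating funds. That is correct, and the point is graded accordingly.

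A reader might go further and infer any of the following, none of which the protocol supports:

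- *The patient form is the only source of visit counts for women who stop treatment.* The separate Arthralgia Module applies at discontinuation too.
- *A percentage of visits is missing.* The protocol gives no share of women under oncologist care and no distribution of visits by doctor. Any product of assumed shares would describe entries on one form, not error in cost, because the eCRF runs in parallel.
- *Only oncologist-treated women are affected.* Without an open category, a visit to any unlisted specialty lacks a field for every woman.
- *The upfront versus switch cost comparison is biased.* That would require the two groups to differ in who treats them, and the protocol gives no information on this.

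**Conclusion.** The point holds as a minor improvement. As listed, both patient questionnaires give gynaecologist visits a field and oncologist visits none, although both specialties run the study. In the patient source, oncologist visits for arthralgia may be omitted or recorded under another specialty.

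The effect reaches the patient-reported part of the descriptive cost evaluation and the patient-reported side of the sick-fund comparison, and goes no further. The co-primary outcomes (compliance and arthralgia score), their tests and the sample size do not depend on this item. The size of the effect cannot be derived from the protocol.

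The conclusion rests on two assumptions: that the forms in Appendices E and F match the lists in Section 8.2, and that some women consult an oncologist because of arthralgia. The second is plausible given the centre types but is not stated.

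**What to change.** In the doctor list of 8.2.1 and 8.2.2, and in Appendices E and F if the lines are absent there, add two answers: 'oncologist, number of times' and 'other doctor (please specify), number of times'. Cost these visits in the same way as the listed ones.

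The cost is two answer lines on each of two paper forms, plus the matching data-entry fields. The burden on patients is negligible. The drawback is that questionnaires already returned will lack the lines, so patient-reported visits collected before and after the change are not fully comparable. The version of the form should therefore be recorded with the data.

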8.2.2 Documentation at 3, 6 an 9 months after study start

The following data should be documented after 3, 6 and 9 months after study start or at the time point of treatment discontinuation

Demographics	Year of birth
Observation interval	Date of assessment
Demographics	Year of birth

Observation interval	Date of assessment
Medication intake	
Daily intake of drugs/tablets apart from the prescribed anti-cancer agent?
 
Number of drugs and tablets per day? (none, unknown)
 
Self reported medication intake (questions from reference): Do you occasionally forget taking of your medicine ? (yes,

	
no)
 
Are you occasionally neglectful concerning your medicine intake? (yes, no)
 
When you feel better, do you occasionally stop taking your medicine? (yes, no)
 
Sometimes when you feel worse, do you stop taking your medicine? (yes, no)
 
How do you feel about taking your medication?
 
 - never mind - don't like it 
Why don't you like taking your medication?
 
 - difficulties in swallowing tablets - disturbs my daily routine - reminds me of my disease - other 
Compliance to anastrozole: You were supposed to take one tablet anastrozole per day. However, daily medication intake may be forgotten. How many anastrozole tablets did you actually take from the start of anastrozole therapy until today:
 
 - none - few - less than half - almost the half - more than half - almost all - all

Questions on arthralgia occurrence, characteristics and management
	
Did you experience any arthralgias during the past three months? (yes, no)
 
Did the arthralgia intensity change during the past three months? (yes, the intensity decreased; yes, the intensity increased; no)
 
Which medication did you take because of arthralgias?
 
Did you consult any doctor because of arthralgias, and in which field did the doctor specify? (general practitioner, number of times; internist, number of times; orthopedist, number of times; rheumatologist, number of times; pain

	therapist, number of times; gynaecologist, number of times) Which diagnostic measures did you undergo during your doctor`s visit? (X-ray, CT, MRT, Ultrasound) Were you admitted to hospital due to arthralgias? Did you receive any physiotherapy? (yes, no, if yes => therapy method; number of prescribed therapies) Performance of any regular sportive action? If yes, how often? VAS scale: Rheumatoid Arthritis Symptom Questionnaire (see appendix F)
Questions about medication side effects	GASE-P: Generic Assessment of Side Effects (appendix F)
Somatosensory amplification of side-effects	SASS, Somatosensory Amplification Scale (appendix F)
Patient`s belief about medicines	BMQ, Beliefs about medicines questionnaire (appendix F)

8.3 Safety measurements and variables

The methods for collecting safety data are described below.

8.3.1 Adverse events (AE)

8.3.1.1 Definitions of AE

An adverse event (AE) is the development of an undesirable medical condition or the deterioration of a pre-existing medical condition following or during exposure to a pharmaceutical product, whether or not considered causally related to the product. An undesirable medical condition can be symptoms (eg nausea, chest pain), signs (eg tachycardia, enlarged liver) or the abnormal results of an investigation (eg laboratory findings, electrocardiogram).

A serious adverse event (SAE) is an AE occurring during the treatment period with anastrozole, that fulfils one or more of the following criteria:

- results in death,
- is immediately life-threatening,
- requires in-patient hospitalisation or prolongation of existing hospitalisation,

- results in persistent or significant disability or incapacity,
- is a congenital abnormality or a birth defect,
- is an important medical event that may jeopardise the subject or may require medical intervention to prevent one of the outcomes listed above.

An unexpected adverse event is an AE not mentioned in the SmPC (see Appendix C).

8.3.1.2 Documentation of AE

All adverse events occurring during the observational period should be documented on the corresponding subject-related AE CRFs. However, events and symptoms which are related to a worsening of the underlying disease to be treated with anastrozole should not be documented as AE.

For each AE, the following information should be given:

- description of adverse event,
- start date of AE,
- stop date of AE,
- maximum intensity of AE [mild, moderate, severe],
- action taken on anastrozole [none, dose reduction, temporarily stopped, stopped],
- outcome [recovered, not yet recovered, permanent disability, death, unknown],
- causality/relationship to anastrozole [no, yes],
- AE serious [no, yes]

8.3.1.3 Reporting of serious adverse events

All SAEs occurring during the observational period must be reported, whether or not considered causally related to anastrozole. However, serious events which are related to a worsening of the underlying disease to be treated with anastrozole should not be documented as a SAE.

When the physician becomes aware of a SAE during the course of the NIS, the physician must immediately (within 24 hours) inform the Patient Safety Department of AstraZeneca GmbH, must document all relevant data on the SAE form (Formblatt "Bericht über unerwünschte Arzneimittelwirkungen", Appendix D), and must send this form to:

AstraZeneca GmbH
Patientensicherheit
[name]
[contact]
[contact]

9. CONDUCT OF THE NIS AND QUALITY ASSURANCE

Before the start of the NIS, each participating physician will be informed in detail about the objectives design and conduct of this NIS, the collection and handling of Informed Consent, the WBDC system, the handling of serious AEs, contact personnel and all other relevant aspects of this NIS. Each participating centre will receive a binder containing the necessary documents and information.

The participation of the physician must be confirmed by signing and dating the project-specific contract between the centre and AstraZeneca GmbH. This contract needs to be signed off by the following persons: participating physician and the AZ representative. The contract needs to be signed in two copies. One signed copy will be retained by the centre and the second signed copy will be filed by AstraZeneca.

Upon completion of the eCRF the investigator declares using a electronic signature form that all data recorded for a patient has been reviewed and are accurate. The digital signature comprises: i. time stamp (date and time of signature), ii. user details (user name and password). The WBDC system is compliant with the FDA (Food and Drug Administration) Code of Federal Regulations (21 CFR Part 11) Electronic Records; Electronic Signatures.

The end of this NIS is defined as the date when the last patient completed the visit scheduled nine months after start of the study.

